16 STATISTICAL METHODS AND CONSIDERATIONS

Overview

This is a prospective, open label, randomized, two-arm, multi-center Phase 3 trial. Enrolled patients with newly diagnosed ITP are randomized at enrollment 2:1 to the experimental treatment arm (eltrombopag) and standard treatment arm (investigator's choice of 3 standard therapies); randomization will be stratified by patient's age at enrollment and up-front treatment status, with block size of 3. Each stratum will be limited to a maximum of 27 patients. Hence, the age distribution of the final accrued cohort may not be representative of the patient population. This is appropriate in the context of this study to ensure sufficient number of patients to study treatment effects in each age group. The primary objective is to determine

whether the proportion of patients with platelet response is greater in the experimental treatment arm compared to the standard therapy arm using a one-sided Cochran-Mantel-Haenszel (CMH) test at alpha=0.025 (see section 16.b).

Intent-to-Treat and Evaluability

For the primary objective, all randomized patients will be included in an intent-to-treat (ITT) analysis. Evaluability for the secondary and exploratory objectives: In the experimental treatment arm, patients will be considered evaluable if they receive at least one dose of eltrombopag. In the standard treatment arm, patients will be considered evaluable if they receive at least one dose of one of the standard of care treatments.

Statistical Analysis

a. Baseline Demographic and Clinical Characteristics

Patient demographic and clinical characteristics at study enrollment will be summarized using descriptive statistics, including frequencies and proportions for categorical measures, and means, medians, ranges, and standard errors for continuous measures.

b. Analysis of Primary Endpoint

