To address the primary objective, we will first test for normality of the distribution of the proportion of platelet responders. If the assumption of normality is upheld, a one-sided Cochran-Mantel-Haenszel (CMH) test, at alpha=0.025, will be used to compare the proportion of platelet responders between the two arms. If the normality assumption is violated, then a one-sided Fisher's exact test will be used. The monitoring boundaries and levels of significance for the interim and final analyses of the primary endpoint are detailed in Table 16A. If a monitoring boundary is crossed in an interim analysis, an independent Data Safety Monitoring Board (DSMB) will make a non-binding recommendation regarding trial conduct or potential closure. In the final analysis, we will reject the null hypothesis if the upper (efficacy) boundary z-value of 1.99302 is crossed; in that case, it will be reasonable to conclude that the rate of platelet response is significantly greater in patients treated with eltrombopag than standard first-line treatments. Otherwise, we will conclude that there is insufficient evidence to support superiority of eltrombopag over standard first-line treatments. All randomized patients will be analyzed in the ITT analysis.

Selection of platelet measurements for the determination of platelet response.

All platelet counts will be reported, and the four measurements closest in time to Weeks 6, 8, 10, and 12 will be selected for the determination of the primary endpoint. Within a sliding one-week window, only one measurement can be selected. Patients who have <3 platelet measurements due to missing data will be classified as non-responders.

c. Analysis of Secondary Endpoints

Analyses of all secondary endpoints will be performed in the subset of evaluable patients. To determine the effects of missing data, sensitivity analyses will be performed using two approaches: a) assuming missing at random; and, b) assuming missing not at random. For each secondary endpoint, the assumption of normality will be tested. If violated for binary endpoints, a Fisher's exact test will be used. If violated for continuous endpoints, a Wilcoxon rank-sum test will be used.

To address secondary objective 3.2.1, the Cochran-Mantel-Haenszel test will be used to compare the proportion of patients with poor WHO Bleeding Score and poor Modified Buchanan Score between the two arms.

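### Secondary efficacy comparisons leave out randomised patients who never started treatment, an avoidable risk of bias in an open-label trial

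*Combined protocol and SAP*

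**What the plan says.** The plan uses two analysis sets. Under Intent-to-Treat and Evaluability, section 16 says: "For the primary objective, all randomized patients will be included in an intent-to-treat (ITT) analysis". For the secondary and exploratory objectives it uses an evaluable set defined separately for each arm. For eltrombopag: "In the experimental treatment arm, patients will be considered evaluable if they receive at least one dose of eltrombopag". For the standard arm: "patients will be considered evaluable if they receive at least one dose of one of the standard of care treatments". Section 16.c then applies this set throughout: "Analyses of all secondary endpoints will be performed in the subset of evaluable patients".

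Two design features matter here. The section 16 overview says: "This is a prospective, open label, randomized, two-arm, multi-center Phase 3 trial". On timing it says: "Enrolled patients with newly diagnosed ITP are randomized at enrollment 2:1". The first dose therefore comes after an assignment that the family and physician know.

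For missing data in the secondary endpoints, section 16.c says that "sensitivity analyses will be performed using two approaches: a) assuming missing at random; and, b) assuming missing not at random". No analysis of the secondary endpoints in all randomised patients is named anywhere.

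**The concern.** Randomisation makes the arms comparable as assigned. A set defined by an event after assignment keeps that comparability only if the event is unrelated to arm or unrelated to outcome. A one-dose rule is easiest to defend when assignment is masked, and here it is not.

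The documents make arm-dependent uptake plausible without reporting it. Section 1 says that each first-line agent has drawbacks in side effects, administration or both, and presents eltrombopag as a once-daily oral alternative. It also notes that some pediatric hematologists already use drugs of this class in newly diagnosed disease. A control family might decline the assigned treatment, a child's count might recover before treatment is given, or a control patient might receive only an agent on the section 7.2.1 prohibited list. Each route can remove a patient from the secondary set, and the routes need not share a prognosis.

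At stake are the between-arm comparisons of bleeding, rescue use, need for ongoing treatment, one-year response, second-line therapy, regulatory T cells, quality of life, fatigue and iron indices. The one-year endpoints bear on the question, raised in section 1, of whether early eltrombopag changes the course of disease. The primary and secondary results would also describe different sets of patients.

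**Working it through.** The plan gives no figure for the size of the evaluable set or for the number never dosed, so there is nothing to reproduce. The text settles that the exclusion exists. The arithmetic below only shows how much it could matter.

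**Does anything restore the excluded patients?** No. Intent-to-treat is tied to the primary objective. The missing-data sensitivity analyses concern missing values and, as written, do not return never-dosed patients to the set. The roughly 9% early loss in section 16.f, assumed similar across arms, is withdrawal from therapy and data submission before week 5. It is not failure to take a first dose.

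**Would the excluded patients have data?** Often. The note closing the section 9 schedules asks for all assessments in enrolled patients even after protocol treatment stops early. Section 12.2 says that subjects who have not left the study should be followed.

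**Illustration.** From the documents: 108 and 54 randomised (section 16.f). Assumed: a binary favourable outcome with true rate 50% in both arms; no undosed eltrombopag patients; a share *u* of controls undosed, at 5%, 10% or 15%; and a success rate *q* among those undosed controls.

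- Dosed controls: 54 × (1 − *u*) = 51.3, 48.6 and 45.9, rounded to 51, 49 and 46.
- Success rate in dosed controls: (0.5 − *u·q*)/(1 − *u*). For *u* = 10% and *q* = 100%: 0.40/0.90 = 44.4%, a false difference of 5.6 points favouring eltrombopag. For *u* = 10% and *q* = 20%: 0.48/0.90 = 53.3%, a false difference of 3.3 points against it.
- False-positive rate: exact binomial enumeration of the pooled two-proportion z test, counting z ≥ 1.96 in favour of eltrombopag. With all 108 and 54 patients and no exclusion it is 2.6%.

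| Success among undosed controls | False difference in points at 5 / 10 / 15% undosed | One-sided false-positive rate |
|---|---|---|
| 100% (worst case) | 2.6 / 5.6 / 8.8 | 4.8 / 9.4 / 16.9% |
| 80% | 1.6 / 3.3 / 5.3 | 3.7 / 5.8 / 8.7% |
| 50% | 0 / 0 / 0 | about 2.5% throughout |
| 20% | −1.6 / −3.3 / −5.3 | 1.6 / 0.9 / 0.5% |

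A positive difference favours eltrombopag. If only one or two of the 54 controls are undosed and all of them succeed, the dosed-control rates are 26/53 = 49.1% and 25/52 = 48.1%, and the false-positive rates are 3.2% and 4.1%. If the undosed share and prognosis are the same in both arms, the false difference is zero.

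**The case against.** The best case for the plan is that few patients will go undosed. Section 6.1 requires a low platelet count, a clinician's judgement that treatment is needed, and equipoise between the arms. Section 8.2.1 makes standard therapy a short course of commercially available drug, with an oral option for some patients. No source supports 5% to 15% undosed. This stands, and it limits the likely size of the problem.

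The direction is also open. A child who recovers before treatment pushes the comparison one way. Nothing shows that families disappointed by their assignment have better outcomes. This stands too.

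The test in the illustration is a stand-in. The plan names Cochran-Mantel-Haenszel tests and ANCOVA, and states no significance level or sidedness for secondary tests. The 2.5% reference is borrowed from the primary analysis.

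Analysing everyone randomised is not a complete cure. Some families who refuse the assigned arm will also withdraw from data submission, and their later outcomes will be missing in any analysis set.

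A reader might infer that randomisation is broken and every secondary result biased. The documents do not support that. Bias requires exclusion that differs by arm and is related to outcome, and neither has been observed. Objective 3.2.3 has no planned between-arm test: section 16.c gives it a proportion and confidence interval in a rescued subset.

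**Conclusion.** The point holds as an avoidable risk of bias in the between-arm secondary efficacy comparisons. The text is clear on the exclusion, on its timing after an open assignment, and on the absence of any all-randomised analysis of these endpoints. The primary analysis is not affected, and a dosed-only set is reasonable for the safety objective 3.2.11.

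The size cannot be computed from the documents. Under the stated assumptions it runs from none to a one-sided false-positive rate of 16.9%, and it can also work against eltrombopag. The 16.9% should not be read as an expected value: it needs 15% of controls undosed, all of them successes, and no undosed eltrombopag patients. The case for acting is that the plan would set aside outcomes that it already intends to collect.

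**What to change.** In section 16, under Intent-to-Treat and Evaluability and in 16.c:

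- Analyse the secondary efficacy endpoints in all randomised patients by assigned arm.
- Keep the at-least-one-dose set for safety (3.2.11) and as a sensitivity analysis for efficacy.
- Report the number never dosed in each arm, with reasons.

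The cost is small but goes slightly beyond a change of wording. Treatment-anchored endpoints need a stated counting origin for never-dosed patients, such as randomisation. The rescue count in 5.2.2 is the clearest case: the plan should say how a standard agent first given late to a control patient is counted. Sections 9 and 12.1 speak of patients who discontinue treatment, so a sentence confirming that follow-up also covers those who never start would help. Outcomes of patients who also withdraw from data submission remain missing and fall to the planned missing-data sensitivity analyses. No new assessments are needed.

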5.2 Secondary Endpoints

- 5.2.1 Poor bleeding score (binary) at 1, 2, 3, 4 weeks, 12 weeks, and 1 year after study enrollment defined as WHO Bleeding Scale ≥ 2 or Modified Buchanan Scale ≥ 3
- 5.2.2 Cumulative number of rescue therapies required during the first 12 weeks of treatment
- 5.2.3 Platelet response (binary), defined as ≥ 3 of 4 weeks with platelets $>50 \times 10^9/L$ during weeks 6-12 of therapy, but patient required a rescue treatment during weeks 1-2 of study
- 5.2.4 No further need for treatment (binary) after 12 weeks or 6 months of study
- 5.2.5 Treatment response (binary endpoints) at 1 year defined as:
 - **CR** is defined as platelet count $>/= 150 \times 10^9/L$
 - **Primary Remission** at 1 year is defined as CR at 1 year with no second-line agents required and $>/= 3$ months after discontinuing most recent platelet active medication
 - **Disease resolution** at 1 year is defined as CR at 1 year $>/= 3$ months after discontinuing most recent platelet active medication. May have received a second-line therapy, excluding rituximab or splenectomy.
 - **Disease stability** at 1 year is defined as platelets $>/= 50 \times 10^9/L$ but $<150 \times 10^9/L$ $>/= 3$ months after discontinuing most recent platelet active medication.
- 5.2.6 Number of 2nd-line therapies (defined in section 7.2.1) in weeks 13-52
- 5.2.7 Absolute change in percentage of CD4⁺25⁺Foxp3⁺ regulatory T cells from baseline at 12 weeks and 1 year
- 5.2.8 Absolute change in parent proxy-reported KIT overall scores from baseline to 1 week, 4 weeks, 12 weeks, and 1 year after study enrollment (see Appendix A2)
- 5.2.9 Total scale intensity ratings (continuous) from the Hockenberry Fatigue Scale-Parent (FS-P) at 1 week, 4 weeks, 12 weeks, and 1 year (see Appendix A2)
- 5.2.10 Serum iron, TIBC, transferrin saturation, ferritin, MCV, and hemoglobin at 12 weeks, 6 months, and 1 year after study enrollment
- 5.2.11 Safety evaluations as defined by:
 - Abnormal LFTs:
 - ALT $\geq 3x$ ULN in patients with normal baseline
 - ALT $\geq 3x$ baseline or $\geq 5x$ ULN (whichever is lower) in patients with abnormal baseline
 - ALT $\geq 3x$ ULN AND bilirubin $\geq 1.5 \times$ ULN ($>35\%$ direct)

- Incidence of adverse events (see section 9.1.6)
- Incidence of serious adverse events (see section 12.2)

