9 STUDY PROCEDURES AND GUIDELINES

EVALUATIONS ¹ WEEK 0-12	SCREENING/DAY 0									UNSCHEDULED VISITS ¹⁰
		72H	W1	W2	W3	W4	W6	W8	W10	
ELIGIBILITY CHECKLIST	x									
PHYSICAL EXAM	x	x ²		x ²				x ²	x	
BLEEDING ASSESSMENT	x	x	x ³	x ³	x			x	x	
TELEPHONE VISIT			x	x						
DEMOGRAPHIC FORM	x									
BASELINE FORM	x									
CONCOMITANT MEDICATIONS	x	x		x			x	x		
OPHTHALMIC ASSESSMENT	x				As needed					
30 DAY FOLLOW-UP ⁴				As needed						
AE/SAE FORM				As needed						
RESCUE MED FORM				As needed						
HRQOL: KIT	x	x		x			x			
HOCKENBERRY FATIGUE SCORE	x	x		x			x			
PROMIS	x						x			
GLOBAL RATE OF CHANGE		x		x			x			
PLATELET COUNT ^{5, 6}	x	x	x	x	x	x	x	x	x ⁶	
CBC ⁵	x				x			x	x	
AST, ALT, TBILI ⁵	x ⁷		x ⁸		x ⁸	x ⁸	x ⁸	x ⁸	x	
DIR COOMBS	x ⁷									
LDH, RETIC ⁵	x ⁷						x			
CREATININE	x ⁷									
PREGNANCY TEST ⁵	x ⁷			x ⁸			x			
FE, TIBC, %SAT FERRITIN ⁵	x ⁷						x			

TREGS ⁹	x	x
SAMPLES FOR BANKING (OPTIONAL)	x	x

¹ 72H time point may occur +/- 24h. Week 1 – Week 4 procedures may occur +/- 72h.

Week 6 – Week 12 procedures may occur +/- 1 week, as long as procedures are separated by at least 1 week:

² Visits may be performed via telehealth when clinically appropriate if necessary for pandemic-related safety or research restrictions

³ Telephone administration of modified Buchanan scale

⁴ Patients will be followed for safety 30 days after the last dose of study treatment

⁵ Local labs (performed at outside lab not associated with ICON site) are acceptable for labs obtained between study visits

⁶ All platelet counts during Week 5 – Week 12 should be reported. Additional platelet measurements between the scheduled Week 6, 8, 10, and 12 measurements should be reported as unscheduled visits.

⁷ May use previously obtained values for screening assessments if done within past 7 days

⁸ Patients on eltrombopag arm only (for duration of eltrombopag administration)

⁹ Performed at central study lab

¹⁰Physical Exam, Bleeding Assessment, Concomitant Medications, Platelet count, and/or CBC to be performed at unscheduled visits when applicable

EVALUATIONS ¹ 4 MOS – 1 YR	4 MOS ²	5 MOS ²	6 MOS	7 MOS ²	8 MOS ²	9 MOS ²	10 MOS ²	11 MOS ²	1 YEAR	UNSCHEDULED VISITS ⁹
PHYSICAL EXAM			x ³				x ³	x		
BLEEDING ASSESSMENT							x	x		
CONCOMITANT MEDICATIONS			x				x	x		
OPHTHALMIC ASSESSMENT					As needed					
AE/SAE FORM					As needed					
RESCUE MED FORM					As needed					
30-DAY FOLLOW-UP ⁴					As needed					

END OF STUDY FORM	x ⁵									
HRQOL: KIT	x									

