To address secondary objective 3.2.2, an ANCOVA model will be used to compare the number of rescue therapies between the two arms.

To address secondary objective 3.2.3, the observed proportion and 95% confidence interval of platelet responders will be calculated in the subset of patients who required a rescue treatment during weeks 1-2 of the study.

To address secondary objective 3.2.4, the Cochran-Mantel-Haenszel test will be used to compare the proportion of patients who do not need ongoing treatment at 12 weeks and 6 months between the two arms.

To address secondary objective 3.2.5, the Cochran-Mantel-Haenszel test will be used to compare the proportion of patients with a treatment response at one year between the two arms.

To address secondary objective 3.2.6, an ANCOVA model will be used to compare the number of 2nd-line therapies between the two arms

To address secondary objective 3.2.7, an ANCOVA model will be used to compare the absolute change from baseline in percentage of regulatory T cells at 12 weeks and 1 year between the two arms

To address secondary objective 3.2.8, KIT scores will be calculated as per the methods described in Klaassen et al.²⁸ Spaghetti plots will be used to visualize the KIT scores over time per patient by treatment arm. An ANCOVA model will be used to compare the absolute change from baseline in KIT overall score at 1 week, 4 weeks, 12 weeks, and 1 year between the two arms. An ANCOVA model will be used to compare the Change Scale score at 1 week, 4 weeks, 12 weeks, and 1 year between the two arms.

To address secondary objective 3.2.9, fatigue scores will be calculated as per the methods described in Hockenberry et al.²⁹ All measures will be rescaled from 0 (no fatigue) to 100 (high fatigue) for consistency in scoring. Spaghetti plots will be used to visualize the fatigue scores over time per patient by treatment arm. The PROMIS tired question: “My child (I) got tired easily never to almost always” will be used as an anchor with severe fatigue defined as “often” or “almost always” with moderate fatigue being “sometimes”. An ANCOVA model will be used to compare the absolute change from baseline in fatigue at 1 week, 4 weeks, 12 weeks, and 1 year between the two arms.

To address secondary objective 3.2.10, an ANCOVA model will be used to compare iron indices at 12 weeks, 6 months, and 1 year between the two arms

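### An iron index that fails the normality test falls back to an unadjusted rank-sum test on the visit value, using neither its screening value nor the randomisation strata

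*Combined protocol and SAP*

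**What the plan says.** Section 16.c sets a general rule for secondary endpoints: "For each secondary endpoint, the assumption of normality will be tested". For continuous endpoints that fail, it continues: "If violated for continuous endpoints, a Wilcoxon rank-sum test will be used". No normality test or significance level is named. The section does not say whether raw values or model residuals are tested, and it offers no transformation, stratified rank test or covariate-adjusted rank method.

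For objective 3.2.10 the planned method is that "an ANCOVA model will be used to compare iron indices at 12 weeks, 6 months, and 1 year between the two arms", with no covariate listed. Section 5.2.10 defines the endpoint as visit values: "Serum iron, TIBC, transferrin saturation, ferritin, MCV, and hemoglobin at 12 weeks, 6 months, and 1 year after study enrollment". By contrast, for objective 3.2.7 the plan will "compare the absolute change from baseline in percentage of regulatory T cells at 12 weeks and 1 year".

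The section 9 schedule marks the row "FE, TIBC, %SAT FERRITIN" at screening. The blood count, which supplies hemoglobin and MCV, is marked there too. The section 16 Overview says "randomization will be stratified by patient's age at enrollment and up-front treatment status", which makes three age groups by two treatment-status groups, or six strata. Secondary analyses use evaluable children; in the experimental arm "patients will be considered evaluable if they receive at least one dose of eltrombopag", with a parallel rule for the standard arm.

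**The concern.** A rank-sum test takes two samples and nothing else. Once an iron index fails the normality check, the ANCOVA is set aside, along with any covariates it would have carried. The visit value contains no baseline information, so the child's own screening value drops out entirely, as do the strata. Under the plan as written, well-behaved indices could be adjusted while the skewed ones, where between-child spread is largest, could not.

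Two things are at stake: power for a named secondary objective examined at three visits, and an adjusted effect estimate with a confidence interval, which the fallback does not supply. Ferritin is the index most likely to trigger the switch if it is right-skewed. That is an assumption, since the documents contain no iron data.

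**Working it through.** **No plan figure to reproduce.** The documents state no power or sample size for iron. The 81.4% in section 16.f concerns the primary endpoint and has no bearing here.

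**Inputs.** From the documents: 2:1 allocation, six strata, and an estimated 98 against 49 informative children (108 against 54 randomised). Assumed: ferritin log-normal with log-SD 0.7, a uniform 20% or 30% fall in one arm, two-sided 0.05, baseline correlation r from 0 to 0.7, and strata unrelated to ferritin unless stated.

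**Closed form, 20% fall.**
- Standardised effect: −ln(0.8)/0.7 = 0.2231/0.7 = 0.319.
- Standard error factor: √(1/98 + 1/49) = 0.175.
- Ratio: 0.319/0.175 = 1.822.
- Rank-sum power: Φ(1.822·√(3/π) − 1.96) = Φ(1.780 − 1.96) = 43%, whatever r is.
- Adjusted power on the log scale: Φ(1.822/√(1 − r²) − 1.96). At r = 0, 0.3, 0.5 and 0.7 the first term is 1.822, 1.910, 2.104 and 2.551, giving 44%, 48%, 56% and 72%.

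**Simulation of the whole procedure, 20% fall** (4,000 runs per cell). The plan is modelled as Shapiro-Wilk on the visit value, then rank-sum if rejected; rejection occurred in every log-normal run. The alternative is log-scale ANCOVA on baseline and strata, moving to rank ANCOVA if the residuals fail Shapiro-Wilk at 0.05.

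| r | Rank-sum fallback | Adjusted | Gain (points) |
|---|---|---|---|
| 0 | 42.7% | 43.8% | 1 |
| 0.3 | 42.4% | 47.6% | 5 |
| 0.5 | 42.3% | 55.5% | 13 |
| 0.7 | 41.9% | 71.3% | 29 |

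**30% fall.** The ratio becomes (0.3567/0.7)/0.175 = 2.912. Rank-sum power is Φ(2.846 − 1.96) = 81%. Adjusted power is 83%, 86%, 92% and 98%, so the gains are about 2, 5, 11 and 17 points. Simulation agrees: 80–81% against 82/86/92/98%. Separate runs put the gain at r = 0.7 between about 15 and 18 points.

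**Sample size.** With 108 against 54 the standard error factor is 0.167 and the 20% ratio is 1.913. The closed-form gains move by less than one point.

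**Strata.** They add nothing if unrelated to ferritin. If they explain 10% of log-variance they add about 3, 2 and 1 points to baseline adjustment at r = 0, 0.3 and 0.5. At 20% they add about 7, 4 and 2.

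**Heavy tails** (log-ferritin t with 4 df, 20% fall, r = 0/0.3/0.5/0.7). Rank-sum 56/57/56/56%; log-ANCOVA alone 46/49/57/74%; log-ANCOVA with rank-ANCOVA fallback 56/59/66/81%. Log-ANCOVA alone can lose about 10 points to the rank-sum test, so the rank fallback is needed.

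**Missing baselines** (r = 0.3; 10/20/30% missing). Complete-case ANCOVA has 42/38/33% power against 42% for rank-sum. With a missing-baseline indicator it has 46/45/45%.

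**Type I error.** With strata explaining 10% of variance, null rejection was 3.4–4.3% for rank-sum and 5.3–5.4% for the adjusted procedure (simulation SE about 0.35). Rank-sum is slightly conservative; there is no clear inflation on either side.

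**Interval available under adjustment.** The 95% factor for the ferritin ratio is exp(1.96·0.7·0.175·√(1 − r²)), about ×/÷ 1.27, 1.26, 1.23 and 1.19 across the four correlations.

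**The case against.** The strongest reply is that nothing here is an error. The rank-sum test is valid, the switch applies only when normality fails, and the matter concerns one of eleven secondary objectives. The correlation that drives the gain is not in the documents. Baseline is taken in newly diagnosed children who need treatment, some after failed first-line therapy, and the outcomes come 12 weeks to one year later, so a low correlation is plausible. The largest gains also come from an operating point near 42% power, where power is most sensitive to precision. All of this stands, and it limits the size of the point.

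Four stronger readings are tempting, and the documents do not support them.
- A reader might infer that the planned ANCOVA ignores baseline. An ANCOVA has a covariate by definition, and baseline is the natural one. The missing covariate list is missing detail, and treating the plan as a covariate-free model would charge it with a method it does not name.
- A reader might infer that normality is tested on raw values. The text allows residuals. Residuals from an untransformed model of a strongly skewed index would be skewed too, so the switch could still follow.
- A reader might infer that iron is uniquely exposed. That holds only on the analysis wording in 16.c, where Tregs, KIT and fatigue are analysed as changes; section 5.2.9 defines fatigue as visit ratings. A change score is no full safeguard either. Relative to ANCOVA its variance is 2/(1 + r), against 1/(1 − r²) for a visit value. At r = 0.3 that is 1.54 against 1.10, so below r = 0.5 an unadjusted test on change scores loses more.
- A reader might take the chelation text in section 7.3 as evidence that the drug alters iron status. It concerns absorption of the drug.

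**Conclusion.** The point holds as a cheap improvement. The substantive problem is the stated fallback: a failed normality check replaces the model with an unadjusted test on the visit value, discards a baseline already collected and the six strata, and leaves no adjusted estimate. It causes no bias or inflated error, and the primary analysis is untouched.

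Under the log-normal assumptions the loss is about 1 to 5 power points at a correlation of 0.3 or less, about 11 to 13 at 0.5, and about 15 to 29 at 0.7, depending on the effect size. Strata related to ferritin would add a few points at low correlation. Because the documents give no iron SD, effect or correlation, these figures illustrate a range and do not estimate this trial's loss.

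**What to change.** In section 16.c, replace the sentence for objective 3.2.10 with:

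> Iron indices at each visit will be compared by ANCOVA with the baseline value of the same index and the randomisation strata as covariates, with ferritin log-transformed at baseline and follow-up. The adjusted ratio (ferritin) or difference (other indices) will be reported with a 95% CI. If the model residuals are clearly non-normal, a rank ANCOVA with the same covariates will be used in place of the Wilcoxon rank-sum test. Children with a missing baseline are kept, using a missing-baseline indicator.

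The SAP should also state how residual normality is judged; Shapiro-Wilk at 0.05 was used in the check above. The same wording could serve the other ANCOVA endpoints that have a baseline.

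The cost is SAP text and a little analysis work, with no new visits, samples or data. There are two downsides. The gain is almost nil if baseline and follow-up are uncorrelated and the strata are unrelated to iron. When the rank fallback applies, its p-value may disagree with the ANCOVA confidence interval.
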